IVRS	Interactive voice response system
LDL-C	Low density lipoprotein cholesterol
LFT	Liver Function Test
Lp(a)	Lipoprotein(a)
MedDRA	Medical dictionary for regulatory activities
OLE	Open label extension
QM	Every month
Q2W	Every 2 weeks
SOC	Standard of care
SAP	Statistical analysis plan
TIA	Transient ischemic attack
ULN	Upper limit of normal
VLDL-C	Very low density lipoprotein cholesterol

1. Introduction

The purpose of this interim SAP is to pre-specify interim analyses to support regulatory filings. The analysis strategy is consistent with the protocol specified analysis. Analyses will be performed based on datasets of an ongoing study 20120138, entitled A Multicenter, Controlled, Open-label (OLE) Study to Assess the Long-term Safety and Efficacy of AMG 145 (latest amendment 2 is 30 APR 2013).

2. Objectives

The objective for this analysis is to summarize the safety and lipid data collected up to a cutoff date reported in the table outputs for subjects rolled over from parent studies into the extension study 20120138. All data prior to the data cut date will be collected, checked and queried in the similar fashion as the final database lock.

3. Endpoints

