5.1 Study Time Points

Baseline

For variables other than sex, race, country, region, and baseline metabolic syndrome, baseline is defined as the parent study baseline. Note that baseline metabolic syndrome will be using parent study baseline information, but with updated sex and race from the extension study data.

First Dose Date

For subjects randomized to AMG 145+SOC, the first dose date is the first date at which the subject was administered IP. For subjects randomized to SOC, the first dose date is the first date at which the subject was administered IP at or after the Week 48 clinical visit.

End of Investigational Product (EOIP) Date

If a subject has completed or discontinued IP, the EOIP date is the date recorded on the final IP dose date eCRF.

End of Study (EOS) Date

For each subject, the End of Study Date is the date recorded on the End of Study eCRF.

Enrollment Date

The enrollment date for a subject is either the subject's EOS date for the parent study or the date that subject has signed the ICF for Study 20120138, whichever is later.

Randomization Date

The randomization date for each subject is the date the investigator (or designee) confirms in the IVRS that the subject has met all eligibility criteria and is randomized.

Study Day 1

For subjects randomized to AMG 145+SOC arm and received at least one dose of AMG 145, Study Day 1 is defined as the first day that AMG 145 is administered during this study.

For subjects randomized to SOC only arm, or randomized to AMG 145+SOC arm but never received AMG 145, Study Day 1 is defined as the day of randomization.

Study Day

For each subject, and for a given study visit date, study day is defined as the number of days since Study Day 1:

$$\text{Study day} = (\text{study visit date} - \text{Study Day 1 date}) + 1$$

If the date of interest is prior to the Study Day 1:

$$\text{Study day} = (\text{study visit date} - \text{Study Day 1 date})$$

SOC-Controlled period

The start of the SOC-Controlled period is Study Day 1.

For the end of the SOC-Controlled period:

- If a subject is administered a dose of IP at Week 48, the day prior to the week 48 IP date is the end of the SOC-Controlled period.
- If a subject is not administered a dose of IP at Week 48, the SOC-Controlled period will end the earliest of Study Day 343, the EOS date, or data cutoff date.

All-IP period

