Appendix A. Analytical Study Week Assignments

Selected endpoints will be summarized by scheduled study visits in descriptive analyses. Since the actual visits may not exactly coincide with their scheduled visit day, the actual visit day is mapped to the study visit generally by non-overlapping consecutive intervals covering the entire time continuum, with scheduled visit time being the center of each interval. The mapping intervals for all distinct schedules are summarized in the following tables. **Week 0 mapping does not pertain to parent study week mapping. Data from the parent studies will use the original analytical weeks in the individual study SAPs.**

Handling multiple records assigned to an analytical study week:

If there is more than one record in a study week interval, the analytical record for that specific study week will be defined as the record closest to the scheduled study day of that specific study week ($7 \times \text{study week} + 1$). If two records are equidistant from the scheduled day, then the earlier record will be chosen. If there are multiple records on the same day, the last record will be used.

Scheduled Visit Week	Vital Signs for AMG 145+SOC group	Vital signs for SOC-only group
Week 0	≤ 1	≤ 1
Week 2	(1, 21]	
Week 4	(21, 42]	
Week 8	(42, 70]	
Week 12	(70, 126]	(1, 126]
Week 24	(126, 210]	(126, End of SOC-controlled period]
Week 36	(210, 280]	
Week 44	(280, 315]	
Week 46	(315, End of SOC-controlled period]	

Scheduled Visit Week	Vital Signs for AMG 145+SOC randomized group	Vital signs for SOC Alone
Week 48	[Beginning of All-IP period, 420]	[Beginning of All-IP period, 343]
Week 50		(343, 357]
Week 52		(357, 378]
Week 56		(378, 406]
Week 60		(406, 462]
Week 72	(420, 546]	(462, 546]
Week 84	(546, 630]	(546, 630]
Week 96	(630, 686]	(630, 686]
Week 100	(686, 707]	(686, 707]
Week 102	(707, 721]	(707, 721]
Week 104	>721	>721

Scheduled Visit Week	Subjects randomized to AMG 145 or Subjects randomized to SOC that were randomized to AMG 145 in parent study		
	Fasting plasma lipids, ApoA1, ApoB, Vitamin E , Chemistry, Hematology, Anti-AMG 145 antibodies, Urinalysis, Urine microalbumin	HbA1c	Body Weight, hsCRP
Week 0	≤ 1	≤ 1	≤ 1
Week 12	(1, 126]	(1, 126]	
Week 24	(126, End of SOC-Controlled period]	(126, End of SOC-Controlled period]	
Week 48	[Beginning of All-IP period, 420]	[Beginning of All-IP period, 532]	[Beginning of All-IP period, 532]
Week 72	(420, 588)		
Week 96	(588, 700]		
Week 104	> 700	>532	>532

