Scheduled Visit Week	Subjects randomized to SOC that were randomized to control in the parent study		
	Fasting plasma lipids, ApoA1, ApoB, Vitamin E , Chemistry, Hematology, Anti-AMG 145 antibodies, Urinalysis, Urine microalbumin	HbA1c	Body weight, hsCRP
Week 0	≤ 1	≤ 1	≤ 1
Week 12	(1, 126]	(1, 126]	
Week 24	(126, End of SOC-Controlled period]	(126, End of SOC-Controlled period]	
Week 48	[Beginning of All-IP period, 378]	[Beginning of All-IP period, 378]	[Beginning of All-IP period, 532]
Week 60	(378, 462]	(378, 574]	
Week 72	(462, 588)		
Week 96	(588, 700]		
Week 104	> 700	>574	>532

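### In this interim SAP no lab, hsCRP or body-weight record can be reported as Week 48 in the controlled-period set, so the by-arm Week 48 LDL-C summary exists only among dosed subjects

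*SAP*

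**What the plan says.** The SAP describes its scope in its Introduction: "The purpose of this interim SAP is to pre-specify interim analyses to support regulatory filings". It is written to protocol Amendment 2.

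- **Period end (SAP 5.1).** "If a subject is administered a dose of IP at Week 48, the day prior to the week 48 IP date is the end"; what ends there is the SOC-Controlled period. If no dose is given at Week 48, the period ends at the earliest of Study Day 343, end of study or data cutoff. All-IP starts the next day. No day range is given for what counts as a dose at Week 48.
- **Week 24 windows (Appendix A).** The bounds are "126, End of SOC-controlled period" in the SOC-only vital-sign column. The lab and HbA1c columns use the same bounds.
- **Week 48 windows (Appendix A).** For lipids and most labs: "Beginning of All-IP period, 420", or "Beginning of All-IP period, 378" for SOC subjects who had control in the parent study. For hsCRP and body weight: "Beginning of All-IP period, 532", with no earlier window after Week 0. For SOC-only vital signs: "Beginning of All-IP period, 343".
- **Several records in one window (Appendix A).** The analytical record "will be defined as the record closest to the scheduled study day of that specific study week", that is, closest to Day 7 × week + 1.
- **Analysis sets (SAP 6).** The ICOAS summarises SOC-Controlled period data whether or not IP was stopped. The IAAS takes randomised subjects dosed with IP and on study in the All-IP period. SAP 8.4.2 runs the LDL-C summaries separately in each set.
- **Protocol (Amendment 6).** LDL-C at Week 48 is a secondary endpoint (10.1.2). The randomised period is analysed on all randomised subjects (10.1.5), and interim analyses of it run up to Week 48 (10.3). At the Week 48 visit SOC-alone subjects take their first dose in clinic, after blood is drawn (6.1.1, 7.1.1.14).

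**The concern.** Week 48 is the last visit at which the two randomised arms can be compared before SOC-alone subjects start AMG 145. Their Week 48 blood is drawn before that first dose, so it is the final untreated control measurement. Under these rules it never appears as Week 48 in the set built for the randomised comparison.

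Three things follow:

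- The Week 48 comparison moves to a set defined by something that happens after randomisation, namely being dosed. A SOC-alone subject who attends Week 48 but declines AMG 145 drops out of it.
- Untreated SOC-alone Week 48 draws count as All-IP data, including in the CK and liver-test incidence tables (SAP 8.4.4).
- hsCRP and body weight have no post-Day 1 controlled-period row at all, because Week 48 would be their only one.

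**Working it through.** **1. The SAP's fixed lab cuts reproduce as midpoints.** The formula is 7 × (week a + week b) / 2.

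| Adjacent weeks | Midpoint | SAP cut |
|---|---|---|
| 12 / 24 | 126 | 126 |
| 48 / 60 | 378 | 378 |
| 48 / 72 | 420 | 420 |
| 48 / 104 | 532 | 532 |
| 60 / 104 | 574 | 574 |
| 72 / 96 | 588 | 588 |
| 96 / 104 | 700 | 700 |
| 24 / 48 | 252 | end of SOC-Controlled period |

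Only the 24/48 boundary departs from the convention.

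**2. Week 48 visit days.** The target is 7 × 48 + 1 = Day 337. With the protocol's 7-day allowance the range is Days 330 to 344, which is 15 days.

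**3. Apply the rules to a lipid or chemistry draw on each of those days.**

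| Week 48 dose relative to draw | Cases | Result |
|---|---|---|
| Same day | 15 of 15 | All-IP, Week 48 |
| 1–7 days before draw | 15 × 7 = 105 of 105 | All-IP, Week 48 |
| 1–7 days after draw | 105 of 105 | SOC-Controlled, Week 24 |
| No dose | 14 of 15 (Days 330–343) | SOC-Controlled, Week 24 |
| No dose | 1 of 15 (Day 344) | All-IP, Week 48 by date; in no analysis set if the IAAS requires a dose within All-IP |

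No case is both in the SOC-Controlled period and labelled Week 48. These are calendar combinations that show how the rule works, not how often each case occurs.

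**4. What happens to a draw placed in the Week 24 window.** The Week 24 target is 7 × 24 + 1 = Day 169. A draw on Day 330 is 330 − 169 = 161 days away, and one on Day 337 is 168 days away. An on-time Week 24 draw is at most 7 days away, so it wins. If the Week 24 draw is missing, the Week 48 value is reported as Week 24. For hsCRP and body weight such a record has no window.

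**5. SOC-only vital signs.** For a subject dosed on Day 344, or not dosed at Week 48 and still on study, All-IP begins on Day 344. The Week 48 window is then [344, 343], which is empty. Day 344 is an allowed visit day.

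**6. The lab fix.** Assign Week 48 to a draw on Day x if 253 ≤ x ≤ U. Take U = 378 for AMG 145 + SOC, and U = the earlier of the first IP dose date and Day 378 for SOC-alone.

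- AMG 145 + SOC: every draw on Days 330–344 qualifies, whatever the dose timing.
- SOC-alone with a same-day dose, a later dose or no dose: x is never after the first dose and is below 378, so every draw qualifies.
- SOC-alone drawn after first dose: x exceeds U, so it is excluded.
- An on-time Week 24 draw (Days 162–176) stays in Week 24.

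**The case against.** The mapping itself is hard to dispute, but its weight can be.

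- **Version.** The SAP is written to Amendment 2 and the protocol supplied is Amendment 6. The schedules differ: the SAP has lab windows at Weeks 72 and 96, whereas the current protocol draws labs at Week 84. A reader might infer that the SAP breaches its protocol. The documents do not support this, because the Amendment 2 wording on endpoints, analysis set and interim analyses is not available. They also do not show that this SAP governs the Week 48 interim analyses of protocol 10.3: it works to a cutoff date, and the ICOAS asks for only about 12 weeks of potential follow-up.
- **Week 48 is still reported.** The IAAS has a by-arm Week 48 row. This stands, so it would be wrong to say that there is no Week 48 comparison. The point is that it covers dosed subjects only.
- **Late dosing in the AMG 145 arm.** The current schedule lists no in-office Week 48 dose for that arm and dispenses IP for home injection, so a dose after the draw is possible. A reader might infer that it is common. In-office doses at Week 44 (QM) and Week 46 (Q2W) make the next dose due at Week 48, so same-day dosing is plausible too, and the Amendment 2 arrangement is not visible.
- **Share of the period.** With a dose on Day 337 the controlled period is Days 1–336, and 336 − 169 = 167 days (49.7%) follow the Week 24 target. A reader might infer that half the period's lab information is lost. Most of that gap exists because no labs are scheduled between Weeks 24 and 48. What is lost is the Week 48 draw.
- **Other tables.** Draws that fall in the Week 24 window still enter the controlled-period shift and CK/liver-test tables, which use periods and not visit windows.

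**Conclusion.** The point holds for the interim tables of this SAP and should be fixed. It follows from the definitions in SAP 5.1, SAP 6 and Appendix A: the ICOAS cannot contain a Week 48 lab, hsCRP or body-weight row, whatever the dosing pattern. The by-arm Week 48 LDL-C summary therefore rests on the dosed-only IAAS, and untreated SOC-alone draws count in the All-IP CK and liver-test incidence.

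In size, one scheduled draw per subject is affected: 1 of 3 post-Day 1 lipid and chemistry draws in the controlled year (Weeks 12, 24, 48), and the only hsCRP and body-weight measurement. The documents do not give the number of subjects who would leave the comparison, or the size or direction of any LDL-C bias.

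The conclusion assumes that period membership is decided by calendar date, as SAP 5.1 is written, and that the ICOAS summaries use only SOC-Controlled period data, as SAP 6 says.

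The analyses are descriptive, and adverse event summaries do not use these windows. A reader might also infer that the protocol's mixed-model estimate at Week 48 is defective. That model is not specified in this SAP, and nothing here shows a fault in it.

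**What to change.** **Labs, HbA1c, hsCRP and body weight (Appendix A).** End the Week 24 lab and HbA1c window at Day 252. Add a randomised-period Week 48 window from Day 253 for lipids, labs, HbA1c, hsCRP and body weight, summarised by randomised arm in the ICOAS. State that it overrides the SAP 5.1 period end for by-visit summaries. Use one upper bound in both arms, for example Day 378, which is already in the lab table. For SOC-alone subjects cut it at the first IP dose date, with the same-day pre-dose draw included. State where records after the bound go; leaving them under the existing All-IP windows is simplest.

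**CK and liver-test incidence.** Count the Week 48 draw of both arms in the SOC-Controlled period only. For SOC-alone subjects count only post-dose draws in All-IP.

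**SOC-only vital signs.** Open the Week 48 window on a fixed day after the Week 36 visit, for example Day 295 (the Week 36/48 midpoint is 7 × 42 = 294), and end the Week 24 window the day before. Keep the Day 343 upper bound, so that the window does not overlap Weeks 50 and 52. A Day 344 visit then falls in the Week 50 row. Opening at Day 253 and running to Day 378 would not work: Day 253 is the Week 36 target, and Day 378 is the end of the Week 52 window.

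**Definitions.** Give the day range within which a dose counts as given at Week 48. State whether the IAAS requires a dose within the All-IP period.

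**Cost.** SAP wording and re-programming of windows, with no new data. The Week 48 row moves from the IAAS to the ICOAS, so any table shell that expects it in the IAAS has to change.

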Subjects with EOS dates or data cutoff dates \leq end of SOC-Controlled period dates will have missing start and end of All-IP period dates.

Otherwise:

- All-IP period start date = end of SOC-Controlled period date+1.
- All-IP period end date = EOS date or the data cutoff date, whichever occurred earlier.

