5.3 Other Study Related Definitions

Analytical Study Week Assignments

Analytical windows will be used to assign parameters to study weeks. The Algorithm is provided in [Appendix A](#).

IP Exposure Period in Months

IP Exposure = $[(\min(\text{EOIP date} + 28 \text{ days}, \text{EOS date}, \text{data cutoff date}) - \text{First dose date}) + 1] / 365.25 * 12$. For subjects randomized to SOC treatment during the SOC-Controlled period, the first dose date is equivalent to the first dose date during the All-IP period.

Study Exposure Period in Months

For each randomized subject, Study Exposure Period = $[\min(\text{EOS date}, \text{data cutoff date}) - \text{enrollment date}] + 1 / 365.25 * 12$

IP Exposure in Months During the SOC-Controlled period

For subjects randomized to AMG 145+SOC arm and received at least one dose of AMG 145 in the SOC-Controlled period, IP Exposure during the SOC-Controlled period = $[(\min(\text{EOIP date} + 28 \text{ days}, \text{end of SOC-Controlled period}) - \text{Study Day 1}) + 1] / 365.25 * 12$. Any IP exposure < 0 will be considered as N/A.

For subjects randomized to SOC or randomized to AMG 145 + SOC and not dosed in the SOC-Controlled period, IP Exposure during the SOC-Controlled period = N/A.

IP Exposure in Months During the All-IP period

For each randomized subject in the Interim All-IP period Analysis Set, IP Exposure during the All-IP period

= $[(\min(\text{EOIP} + 28 \text{ days}, \text{end of All-IP period}) - \text{start date of All-IP period}) + 1] / 365.25 * 12$. If the above calculation is < 0 , then set to 0.

Study Exposure in Months During the SOC-Controlled period

For each randomized subject, Study Exposure Period for the SOC-Controlled period = $[(\text{end of SOC-Controlled period date} - \text{start of the SOC-Controlled period}) + 1] / 365.25 * 12$.

Study Exposure in Months During the All-IP period

For each randomized subject that received a dose of IP during the All-IP period,

Study Exposure Period for the All-IP period = $[(\text{end of All-IP period} - \text{start of the All-IP period}) + 1] / 365.25 * 12$.

Adverse Events Included in the Summary Tables

An adverse event is included in SOC-Controlled period summaries if it occurs during the SOC-Controlled period and the subject is in the Interim SOC-Controlled period Analysis Set.

An adverse event is included in All-IP period summaries if it occurs during the All-IP period and the subject is in the Interim All-IP period Analysis Set.

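### For SOC-alone subjects first dosed after Week 48, the All-IP exposure formula counts days before the first dose as IP exposure

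*SAP*

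**What the plan says.** SAP section 5.1 (Study Time Points) closes the SOC-Controlled period by one of two rules:

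- "If a subject is administered a dose of IP at Week 48, the day prior to the week 48 IP date is the end".
- "If a subject is not administered a dose of IP at Week 48, the SOC-Controlled period will end the earliest of Study Day 343". If study end or data cutoff comes sooner, that date is used instead.

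The next period then follows without reference to dosing: "All-IP period start date = end of SOC-Controlled period date+1".

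For the SOC arm, the same section defines the first dose date as the "first date at which the subject was administered IP at or after the Week 48 clinical visit". A first dose later than that visit is thus foreseen.

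SAP section 5.3 gives three IP-exposure figures for a SOC-alone subject:

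- Overall IP exposure starts at the first dose date: "For subjects randomized to SOC treatment during the SOC-Controlled period, the first dose date is equivalent to the first dose date during the All-IP period".
- In the control period: "IP Exposure during the SOC-Controlled period = N/A".
- In the All-IP period, exposure starts at the start date of that period.

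Section 5.3 also puts into the All-IP summaries any adverse event that occurs in the period in a member of the Interim All-IP period Analysis Set (IAAS). Section 6 requires only that the member was dosed and on study in the period, and takes data from the start of the period. Section 8.4.7 reports patient-months of IP exposure for each analysis set and overall.

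**The concern.** A SOC-alone subject receives no AMG 145 in this study before the switch. All of that subject's IP exposure lies in the All-IP period, so the All-IP figure and the overall figure should be equal. Under the two start dates they are not: for a late starter, the exposure in one period is larger than the exposure in the whole study.

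Two outputs are at stake. The patient-month table for the IAAS would include time before any dose. The All-IP adverse event tables would include events from that time. Adverse event incidence is the primary endpoint, and SAP section 8.4.1 singles out injection site reactions and hypersensitivity, which days before the first injection cannot inform. The SAP supports interim regulatory filings, and at an early cutoff the extra days are a larger share of each late starter's exposure.

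**Working it through.** **Where Day 343 appears to come from.** SAP Appendix A places a visit at study day 7 × week + 1, so Week 48 is 7 × 48 + 1 = Day 337. Protocol section 7.1.1.14 allows ±7 days, giving Days 330 to 344. The day before the last window day is 343, which matches the SAP's cap. For a subject not dosed at Week 48 and still on study, the All-IP period therefore starts on Day 344.

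**The two exposure formulas (SAP section 5.3).**

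- All-IP: [min(EOIP + 28 days, end of All-IP period) − start of All-IP period + 1] / 365.25 × 12
- Overall: [min(EOIP + 28 days, EOS, cutoff) − first dose date + 1] / 365.25 × 12

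The end of the All-IP period is itself the earlier of EOS and cutoff, so both formulas end on the same day. They differ only in the start:

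excess = (first dose day − 344) / 365.25 × 12 months.

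| First dose (not counted as the Week 48 dose) | Excess days | Excess months |
|---|---|---|
| Day 351 | 7 | 0.23 |
| Day 365 | 21 | 0.69 |
| Day 393 | 49 | 1.61 |

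**One subject in full (assumed dates).** First dose on Day 365:

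- Exposure ends on Day 730: All-IP (730 − 344 + 1) / 365.25 × 12 = 12.71 months; overall (730 − 365 + 1) / 365.25 × 12 = 12.02 months. The excess is 21/366 = 5.7%.
- Exposure ends on Day 450, as at an early cutoff: All-IP 107 / 365.25 × 12 = 3.52 months; overall 86 / 365.25 × 12 = 2.83 months. The excess is 21/86 = 24.4%.

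In both cases, events on Days 344 to 364 enter the All-IP tables.

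**Aggregate, by assumption only.** Protocol section 10.2 expects 4428 subjects. With 2:1 randomization, about 4428/3 = 1476 are SOC-alone. The documents give no late-start rate. Assuming 2% late starters with a 7-day gap, the excess is 1476 × 0.02 × 7 / 365.25 = 0.6 person-years. Assuming 20% with a 77-day gap, it is 1476 × 0.20 × 77 / 365.25 = 62 person-years.

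**A related sign.** In SAP Appendix A, the Week 48 vital-signs window for SOC-alone subjects runs from the beginning of the All-IP period to Day 343. Under the cap it runs from Day 344 to Day 343 and is empty. The cap was not carried through for this arm.

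**The case against.** Much can be said for leaving the text alone, and most of it limits the point.

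- **Incidence denominators.** A reader might infer that drug-free time dilutes the adverse event results. The SAP does not support that. The primary endpoint is subject incidence, its denominator is the number of IAAS subjects, and no exposure-adjusted rate is planned. What remains is the descriptive patient-month table, and possible extra subjects with an event in the All-IP numerators.
- **Attribution to drug.** A reader might also infer that pre-dose events are ascribed to AMG 145. All-IP is a study period that runs to EOS or cutoff, so it also keeps events after IP is stopped. Tables are by randomized and parent-treatment group, and relatedness is assessed separately by the investigator (Protocol section 9.1.2). Including pre-dose events is imprecise, but it is not a causal claim.
- **Who is affected.** It is tempting to say that every SOC-alone subject dosed after Day 344 is affected. The SAP does not define a dose at Week 48. If it means the dose given at the Week 48 visit, a subject whose visit and dose fall on Day 365 starts All-IP on Day 365 with no drug-free days. The excess arises only when the first dose is not the Week 48 dose. Protocol section 7.1.1.14 schedules that first injection at the Week 48 visit, so late starters may be few, and subjects never dosed are outside the IAAS.
- **A correct figure exists.** Overall IP exposure already starts at first dose. That is true, but the All-IP figure reported beside it would still disagree.

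**Conclusion.** The point holds in a narrow form. For a SOC-alone subject who is not dosed at Week 48 and starts AMG 145 later, the All-IP IP-exposure formula reports days before the first dose as IP exposure. It exceeds the same subject's overall IP exposure by (first dose day − 344) days. Events on those days enter the All-IP adverse event tables. This follows from the SAP's definitions alone.

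The effect per subject is known: 0.23 to 1.61 months for first doses on Days 351 to 393. The aggregate effect is not known, because the documents do not give the number of late starters; it is probably small if most subjects are dosed at Week 48 as scheduled. The examples assume that these doses do not count as Week 48 doses. Drug-free here means no AMG 145 in this study, since some SOC-alone subjects received it in the parent study. This is a minor correction to a formula that gives a wrong figure as written.

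**What to change.** 1. Keep the Day 343 cap on the SOC-Controlled period in both arms.
2. In SAP section 5.3, for SOC-alone subjects, use max(start of All-IP period, first dose date) as the start in the All-IP IP-exposure formula. The excess becomes 0 and the two exposure figures agree.
3. Apply the same start to the All-IP adverse event inclusion rule for these subjects, and report events from Day 344 to the day before first dose separately.
4. State in section 5.1 whether dosing at Week 48 means the dose given at the Week 48 visit or a dose within a stated day window.

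An apparent alternative is to extend the SOC-Controlled period to the day before first dose, or to EOS or cutoff if there is none. It should be avoided. It would lift the cap in the SOC-alone arm only, so undosed control subjects could add control-period events up to EOS or cutoff while AMG 145 + SOC subjects not dosed at Week 48 stay capped at Day 343. That would bias the randomized comparison.

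The cost is a few lines of SAP text and a small separate listing of pre-dose events.
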